### 3.3 SCHEDULE OF EVENTS

#### 3.3.1 Schedule of Events for Study Part A

	Phase	Screening	Check-in	Treatment Period 1					Treatment Period 2					Treatment Period 3				
Procedure (a)	Day/Treatment	D-28 to -1	Day -1	D1	D2	D3	D4	D5	D8	D9	D10	D11	D12	D15	D16	D17	D18	D19/EOS
Admission to clinic			X															
Discharge from the clinic/study																		X
Informed consent		X																
Demographics		X																
Serology (b)		X																
Serum FSH (c)		X																
Inclusion/exclusion criteria		X	X															
Medical history		X	X															
Height, weight, and BMI (d)		X	X	X					X					X				X
Physical examination (e)		X	X	X					X					X				X
Vital sign measurements (f)		X	X	X	X	X	X	X	X	X	X	X	X	X	X	X	X	X
12-lead ECG (g)		X		X					X					X				X
Clinical laboratory testing (h)		X	X				X					X					X	X
Urinalysis (h)		X	X				X					X					X	X
Urine drug/alcohol/cotinine screen (i)		X	X															
Pregnancy test (j)		X	X															X
Sample for pharmacogenomics		X																
Study drug administration (k)				X					X					X				
PK sample collection (l)				X	X	X	X	X	X	X	X	X	X	X	X	X	X	X
Urine PK sample collection (m)				X	X				X	X				X	X			
Adverse events (n)		X																
Prior/concomitant medications (o)		X																

Abbreviations: AEs, adverse events; BCRP, breast cancer resistance protein; BMI, body mass index; D, day; ECG, electrocardiogram; EOS, end of study; FSH, follicle-stimulating hormone; PD, pharmacodynamic; P-gp, P-glycoprotein; PK, pharmacokinetic; QTcF, QT interval corrected for heart rate using Fridericia's formula

Notes:

- When procedures are scheduled for the same timepoint ECG should be performed first, followed by vital sign assessment, urine collection, meal, blood collection, and dose (in that order).
- A complete list of serology assessments is provided in Section 6.2.3.
- Females only. Further details are provided in Section 6.2.3.

- d) Height and weight will be measured, and BMI calculated at screening only. Only weight will be measured at check-in, dosing, and EOS.
- e) A full physical examination will be performed at screening and check-in. A symptom-driven physical examination may be performed at other times, at the investigator's or designee's discretion. Further details are provided in Section 6.2.6.
- f) Further details on vital signs (respiratory rate, body temperature, pulse rate, and blood pressure) measurements are provided in Section 6.2.4.
- g) ECG should be recorded at screening, predose within 2 hours on each dosing day, and at EOS. Further details on ECG recordings are provided in Section 6.2.5.
- h) Clinical laboratory testing will occur at screening, check-in, 3 days from dosing (Day 4, 11, 18), and at EOS. If any concerning trends are seen during study, the investigator can order additional testing for safety on PRN basis. Further details on clinical laboratory assessments, including a complete list of assessments, are provided in Section 6.2.3.
- i) Further details are provided in Section 6.2.3.
- j) Urine pregnancy test to be done at screening. Serum pregnancy test to be done at check-in, and at EOS.
- k) Further details on dosing of study treatments are provided in Section 5.1.
- l) Further details on the collection of blood samples for PK analysis are provided in Section 6.1 and in Table 6-1.
- m) Further details on the collection of urine samples for PK analysis are provided in Section 6.1 and in Table 6-2.
- n) Further details on collection and reporting of AEs are provided in Section 6.2.
- o) Information regarding prior medications taken by the participant within the 30 days before signing the ICF will be recorded in the participant's eCRF. Details regarding prior and concomitant medications are provided in Section 5.5.1.

### 3.3.2 Schedule of Events for Study Part B

	Phase	Screening	Check-in	Treatment Period 1					Treatment Period 2					Treatment Period 3				
Procedure (a)	Day/Treatment	D-28 to -1	Day -1	D1	D2	D3	D4	D5	D8	D9	D10	D11	D12	D15	D16	D17	D18	D19/EOS
Admission to clinic			X															
Discharge from the clinic/study																		X
Informed consent		X																
Demographics		X																
Serology (b)		X																
Serum FSH (c)		X																
Inclusion/exclusion criteria		X	X															
Medical history		X	X															
Height, weight, and BMI (d)		X	X	X					X					X				X
Physical examination (e)		X	X	X					X					X				X
Vital sign measurements (f)		X	X	X	X	X	X	X	X	X	X	X	X	X	X	X	X	X
12-lead ECG (g)		X		X					X					X				X
Clinical laboratory testing (h)		X	X	X			X		X			X		X			X	X
Urinalysis (h)		X	X	X			X		X			X		X			X	X
Urine drug/alcohol/cotinine screen (i)		X	X															
Pregnancy test (j)		X	X															X
Sample for pharmacogenomics		X																
Study drug administration (k)				X					X					X				
PK sample collection (l)				X	X	X	X	X	X	X	X	X	X	X	X	X	X	X
Adverse events (m)										X								
Prior/concomitant medications (n)										X								

Abbreviations: AEs, adverse events; BCRP, breast cancer resistance protein; BMI, body mass index; D, day; ECG, electrocardiogram; EOS, end of study; FSH, follicle-stimulating hormone; PD, pharmacodynamic; P-gp, P-glycoprotein; PK, pharmacokinetic; QTcF, QT interval corrected for heart rate using Fridericia's formula

Notes:

- When procedures are scheduled for the same timepoint ECG should be performed first, followed by vital sign assessment, urine collection, meal, blood collection, and dose (in that order).
- A complete list of serology assessments is provided in Section 6.2.3.
- Females only. Further details are provided in Section 6.2.3.
- Height and weight will be measured, and BMI calculated at screening only. Only weight will be measured at check-in, dosing, and EOS.
- A full physical examination will be performed at screening and check-in. A symptom-driven physical examination may be performed at other times, at the investigator's or designee's discretion. Further details are provided in Section 6.2.6.
- Further details on vital signs (respiratory rate, body temperature, pulse rate, and blood pressure) measurements are provided in Section 6.2.4.

- g) ECG should be recorded at screening, predose within 2 hours on each dosing day, and at EOS. Further details on ECG recordings are provided in Section 6.2.5.
- h) Clinical laboratory testing will occur at screening, check-in, predose within 2 hours on each dosing day, 3 days from dosing (Day 4, 11, 18), and at EOS. If any concerning trends are seen during study, the investigator can order additional testing for safety on PRN basis. Further details on clinical laboratory assessments, including a complete list of assessments, are provided in Section 6.2.3.
- i) Further details are provided in Section 6.2.3.
- j) Urine pregnancy test to be done at screening. Serum pregnancy test to be done at check-in, and at EOS.
- k) Further details on dosing of study treatments are provided in Section 5.1.
- l) Further details on the collection of blood samples for PK analysis are provided in Section 6.1 and in Table 6-1.
- m) Further details on collection and reporting of AEs are provided in Section 6.2.
- n) Information regarding prior medications taken by the participant within the 30 days before signing the ICF will be recorded in the participant's eCRF. Details regarding prior and concomitant medications are provided in Section 5.5.1.

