### **6.2.3 Clinical Laboratory Testing**

Clinical laboratory testing will occur at screening, check-in, predose within 2 hours on each dosing day (Days 1, 8, and 15) (for Part B only), 3 days from dosing (Day 4, 11, 18), and at EOS. Clinical laboratory tests will be performed by the PPD Central Laboratory. Blood and urine samples will be collected under fasting conditions and will be prepared using standard procedures. If any concerning trends are seen during study, investigator can order additional testing for safety on PRN basis.

Repeat clinical laboratory tests may be performed at the discretion of the investigator, if necessary, to evaluate inclusion and exclusion criteria or clinical laboratory abnormalities. The clinical laboratory that will perform the tests will provide the reference ranges for all clinical laboratory parameters. Abnormal clinical laboratory values will be flagged as either high or low (or normal or abnormal) based on the reference ranges for each laboratory parameter.

The following clinical laboratory assessments will be performed:

Hematology	Absolute neutrophil count and differential, hematocrit, hemoglobin, mean corpuscular hemoglobin, mean corpuscular hemoglobin concentration, leukocytes-absolute counts and percentages (basophils, eosinophils, lymphocytes, monocytes, neutrophils), mean corpuscular volume, platelet count, red blood cell count, and red cell distribution width
Serum Chemistry	Alanine aminotransferase, albumin, alkaline phosphatase, aspartate aminotransferase, bilirubin (total + indirect and direct fractions), blood urea nitrogen, calcium, carbon dioxide, chloride, creatinine, gamma-glutamyltransferase, globulin, glucose, lactate dehydrogenase, phosphorus, potassium, sodium, total protein, uric acid, and creatine kinase
Urinalysis	Appearance, bilirubin, color, glucose, ketones, leukocytes, reflex microscopy (performed if dipstick is positive for protein or the blood value is 1+ or greater; and includes bacteria, casts, crystals, epithelial cells, red blood cells, and white blood cells), nitrites, occult blood, pH, protein, specific gravity, turbidity, and urobilinogen
Serology	Hepatitis B surface antigen, hepatitis C virus antibody, and human immunodeficiency virus antibody types 1 and 2 (screening only)

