### **7.3.2 Safety Analyses**

Adverse events will be coded by preferred term and system organ class using the latest version of MedDRA. All AE data will be presented in a data listing. TEAEs will be summarized by treatment and overall, as well as by severity, seriousness, and relationship to study drug. Serious

AEs and AEs leading to discontinuation of study drug will also be presented in the data listings and summarized by treatment and overall.

Actual values and changes from baseline for clinical laboratory test results, vital sign measurements, and 12-lead ECG results will be summarized by treatment at each time point using descriptive statistics (number of participants, mean, SD, median, minimum, and maximum). Physical examination findings will be presented in a data listing.

For safety analysis, unless stated otherwise, baseline will be defined as the last nonmissing assessment (including repeat and unscheduled assessments) predose for each period. An overall baseline for by-sequence analysis will be defined as the last value prior to Day 1 dose.

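### Part B's procedure order lists the meal before blood collection while safety labs must be fasting, so up to 36 of 48 period baselines for hematology and chemistry could be post-meal

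*Protocol*

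**What the plan says.** Four statements bear on this point.

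- **Procedure order.** Protocol Section 3.3.2 (Part B), note a, applies when procedures fall at the same timepoint. It puts ECG first, "followed by vital sign assessment, urine collection, meal, blood collection, and dose (in that order"). The SAP's Part B schedule (Section 13, note a) has the same sentence.
- **Fasting rule.** Protocol Section 6.2.3: "Blood and urine samples will be collected under fasting conditions and will be prepared using standard procedures". It makes no exception for fed dosing days.
- **Dosing-day labs.** The same section adds draws "predose within 2 hours on each dosing day (Days 1, 8, and 15) (for Part B only"), and note h of the Part B schedule agrees. The Part A schedule has no safety labs on dosing days.
- **Baseline.** Protocol Section 7.3.2: "baseline will be defined as the last nonmissing assessment (including repeat and unscheduled assessments) predose for each period". SAP Section 4 uses the same rule, and SAP Section 8.2 tabulates hematology and chemistry change from baseline by treatment.

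Protocol Section 3.2 gives a pre-dose meal in Treatments B, C and D. Only Treatment A is fasted.

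**The concern.** In Part A the only blood due before dosing on a dosing day was the PK sample, so listing the meal ahead of blood collection caused no conflict with the fasting rule. Part B uses the same sentence but adds safety labs to those mornings. It may simply have been carried over, though that is an inference.

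Read literally, the note has safety blood in a fed period drawn after the meal, and that draw then becomes the period's baseline. The later samples it is compared with (Days 4, 11 and 18, and end of study) fall under the fasting rule in every treatment. For any analyte that responds to food, the change from baseline would then carry a meal component in B, C and D and none in A. Glucose is the plain example, and it is on the chemistry panel. The distortion would line up with food, the factor Part B is designed to study.

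**Working it through.** The plan states no figure on this point, so there is none to reproduce. The check has four steps.

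**1. Does note a reach the safety labs?**
- Notes g and h of the Part B schedule give ECG and safety labs the same timing: before dosing, within 2 hours, on each dosing day. On that wording they share a timepoint.
- The note's own list includes the meal and the dose, which cannot happen at the same minute. It therefore reads most naturally as covering the whole predose block.
- No Part B text restricts blood collection to PK.

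The note can be read as covering safety blood, but the documents do not settle it.

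**2. How many baselines could be affected?**
Inputs: 16 participants, four sequences at 1:1:1:1 (A:C:D, B:D:A, D:B:C, C:A:B), three periods each (SAP Section 3.2). Full enrolment and no dropout are assumed.
- Participants per sequence: 16 / 4 = 4.
- Period baselines: 16 × 3 = 48.
- Each treatment appears in 3 of the 4 sequences: 3 × 4 = 12 baselines per treatment.
- Fed treatments B, C and D: 3 × 12 = 36, and 36 / 48 = 75%.
- Fasted treatment A: 12, and 12 / 48 = 25%.
- Three of the four sequences contain A, so 3 × 4 = 12 participants could have a mix of fed and fasting baselines.

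**3. What happens to the change from baseline?**
Let δ be the shift a post-meal draw causes in an analyte, and f the share of a fed treatment's baseline draws taken after the meal. The mean change at Day 4, 11 or 18 then moves by −f × δ in that treatment and by 0 in Treatment A.
- If every site draw precedes the meal, f = 0 and nothing changes.
- If note a is followed throughout, f = 1 and the shift is −δ.

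The documents give neither f nor δ, and δ could differ between the high-fat and low-fat meals.

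**4. Would a fasting draw fit the schedule?**
Dosing is 30 ± 5 minutes after the meal starts (protocol Section 3.2), so the meal starts 25 to 35 minutes before dosing. The lab window is 120 minutes.
- Time in the window before the meal: 120 − 35 = 85 to 120 − 25 = 95 minutes, or 71% to 79% of it.
- Vital signs are taken 60 to 90 minutes before dosing (Section 6.2.4). From then to the meal there are 60 − 35 = 25 to 90 − 25 = 65 minutes.
- If the full 30 minutes allowed for eating are used, the time from end of meal to dose is 25 − 30 = −5 to 35 − 30 = +5 minutes.

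A fasting draw fits easily. A draw between the end of the meal and the dose may not fit at all. The predose PK sample is due within 15 minutes before dosing (Table 6-1), so it necessarily follows the start of the meal.

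**The case against.** The strongest reply is that note a is a tie-break, not a fixed sequence. It opens with a condition about procedures at the same timepoint, while vital signs, meal, labs and PK sample each have their own window. Section 6.2.3 states the dosing-day labs and the fasting rule in one paragraph, and all participants fast overnight for at least 10 hours. A site that treats labs and meal as separate timepoints can satisfy every instruction by drawing before the meal. This stands, and it rules out saying that the baselines will be post-meal or that the two rules can never both be met. It does not remove the ambiguity, because nothing tells the site which instruction has priority.

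The SAP's Part A note a is sometimes a help here: it has blood draws follow ECG or vital signs and places PK sampling last. That shows blood draws and PK samples are distinct in the authors' usage. But it is Part A text, and it also puts the meal before blood collection, so it does not decide the matter for Part B.

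Two mitigations also stand. SAP Section 8.2 adds a hematology and chemistry summary with a baseline on or before check-in (Day -1), which precedes every study meal and dose. And the laboratory tables are descriptive: no test or decision rule uses them. The adverse events of special interest concern bilirubin, ALT and AST, for which no meal effect is claimed here.

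A reader might also infer a specific glucose bias, or that the purpose of the dosing-day labs is defeated. The documents support neither: they give no analyte shift and do not say why those labs were added.

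**Conclusion.** The point holds in conditional form. Part B note a and the fasting rule in Section 6.2.3 need to be reconciled for safety blood in Treatments B, C and D. If the note is applied to that blood, up to 36 of 48 hematology and chemistry baselines could be post-meal while the 12 for Treatment A are fasting. The main by-treatment change summaries would then mix two kinds of comparison.

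The count of 36 is a ceiling. It rests on 16 participants completing three periods and on every fed-period draw following the meal. The size of the resulting shift is unknown. ECG, vital signs and urine come before the meal in the stated order and are unaffected, as is the SAP's Day -1 baseline summary. Part A is not involved. The change is worth making because any distortion would follow the treatment factor and is easily avoided.

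**What to change.** Reorder Part B note a, in protocol Section 3.3.2 and SAP Section 13, to agree with Section 6.2.3:

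ECG; vital signs; urine; fasting safety-laboratory blood; meal (Treatments B, C and D); predose PK sample, within 15 minutes before dosing; dose.

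This separates the two kinds of blood draw, so that only the PK sample follows the meal. The cost is one footnote in each document. It adds no procedure, and the draw fits the existing 2-hour window.

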## 4. STUDY POPULATION

Approximately 12 participants in Part A and 16 participants in Part B will be enrolled at a single center in the United States.

### 4.1 INCLUSION CRITERIA

Each participant must meet all the following criteria to be enrolled in this study:

1. The participant is able to provide written informed consent.
2. Healthy male or non-pregnant, non-lactating female participants aged 18 to 55 years, inclusive, with a BMI of 18 kg/m^2 or greater, but less than 30 kg/m^2. The participant is considered by the investigator to be in good general health status as determined by physical examination, vital signs, temperature, medical history, no clinically significant abnormalities at investigator's discretion in laboratory and urine analyses and with normal organ function as defined below:
  - Normal renal function: creatinine clearance  $\geq 90$  mL/min
  - Normal liver enzymes and bilirubin ( $\leq$ ULN)
  - ECG, with QTcF interval  $\leq 450$  msec; at screening.
3. Healthy female participants must be:
  - a) Documented to be surgically sterile (surgical methods inclusive of hysterectomy, bilateral salpingectomy, and/or bilateral oophorectomy) or postmenopausal (amenorrhea for  $\geq 24$  months without an alternative medical cause and FSH  $\geq 30$  mIU/mL).
  - OR**
  - b) Using contraception, including 1 highly effective nonhormonal methods (eg, intrauterine device) in combination with a barrier contraception (eg, male or female condoms, diaphragm, spermicide, etc.) from start of plixorafenib administration until 30 days after the last plixorafenib administration, and having a negative serum or urine  $\beta$ -hCG pregnancy test (with a sensitivity of at least 25 mIU/mL) at screening and check-in.
4. Male participants with female partners of childbearing potential must be sterile (confirmed by documented azoospermia 90 days after the procedure) or agree to use (from check-in until 90 days after discharge) one of the following approved methods of contraception: male condom with spermicide; sterile sexual partner (males must still agree to use condom with their surgically sterile female partner if unable to provide documentation of partner's sterility); or practice abstinence (abstinence is acceptable only as true abstinence when this is in line with the preferred and usual lifestyle of the participant, periodic abstinence won't be allowed); or use of an intrauterine device with spermicide by female sexual partner; a female condom with spermicide; a contraceptive sponge with spermicide; an intravaginal system; a diaphragm with spermicide; a cervical cap with spermicide; or oral, implantable, transdermal, or injectable contraceptives.

5. Male participants must refrain from sperm donation and female participants must refrain from egg donation from check-in until 90 days after discharge from the study.
6. The participant agrees to comply with all protocol requirements for the duration of the study.

## 4.2 EXCLUSION CRITERIA

Participants meeting any of the following criteria will be excluded from the study:

1. The participant has a history of clinically significant drug allergy or anaphylaxis, including known hypersensitivity to any components of plixorafenib or cobicistat.
2. The participant has a history of any condition(s) or gastrointestinal surgeries, including gallbladder procedures, which might affect drug absorption, metabolism, or excretion.
3. The participant has clinical evidence or a history of clinically significant cardiovascular, respiratory, renal, hepatic, gastrointestinal, hematological, neurologic, or other chronic disease as judged by the investigator.
4. The participant has a history of psychiatric disease, a suicidal attempt, hospitalization for psychiatric disease, a period of disability due to a psychiatric disease, or administers treatment to control the condition. Psychiatric disease includes major depression, bipolar disorder, or psychosis for  $\geq 3$  months.
5. The participant has a history or other evidence of illness, test abnormalities, or any other conditions which would make the participant, in the opinion of the investigator, unsuitable for the study.
6. The participant has any history of alcoholism or drug abuse, or excessive alcohol consumption (regular alcohol intake  $> 21$  units per week for male participants and  $> 14$  units of alcohol per week for female participants) (1 unit is equal to approximately  $\frac{1}{2}$  pint [200 mL] of beer, 1 small glass [100 mL] of wine, or 1 measure [25 mL] of spirits) within 3 months before screening.
7. The participant has positive results on screen for drugs of abuse or alcohol (Section 6.2.3 [Other analyses]) at screening visit or Day -1.
8. The participant is a smoker or has used nicotine or nicotine-containing products (eg, snuff, nicotine pouch (eg, ZYN), nicotine patch, nicotine chewing gum, mock cigarettes, or vape cigarette alternatives, inhalers), marijuana, and cannabinoids within 1 year before the first dose of study drug.
9. The participant has donated blood in the past 90 days prior to screening or has poor peripheral venous access.
10. The participant has a diagnosis of chronic or acute liver disease, for example, auto-immune, alcoholic, or neoplastic liver disease.

11. The participant has positive serostatus for HIV, HCV, or HBV.
12. Male partners of females who are pregnant.
13. Female participant of childbearing potential who is pregnant, lactating, or planning to become pregnant within 90 days after the last dose of study drug.
14. The participant has received an investigational drug, biologic, or device within 3 months or 5 half-lives of the investigational drug (whichever is longer), before receiving study drug.
15. The participant has used any systemic medications, including vitamins and over-the-counter items, during the 14 days (or 5 times the elimination half-life of the medication, whichever is longer) before receiving study drug or will require their use during the study. Inducers and inhibitors of metabolic enzymes and/or transporters (in particular CYP3A inhibitors or inducers, P-gp, and BCRP), and herbal preparations, nutritional supplements (eg, St. John's Wort), or foods, including grapefruit juice, grapefruit/grapefruit-related citrus fruits (eg, Seville oranges, pomelos), which have been shown to produce metabolic enzyme or transporter induction or inhibition, are prohibited before 5 half-lives of the investigational drug prior to check-in (Day -1). Paracetamol  $\leq 3000$  mg/day will be allowed up to 2 consecutive days before dosing and during the outpatient phase of the study, as needed.
16. The participant has been on a diet incompatible with the on-study diet, in the opinion of the investigator or designee, within 30 days prior to the first dosing and throughout the study.
17. The participant is part of the clinical staff personnel or a family member of the clinical site staff.

